12.2 Halting Criteria for Sentinel Group

The study will be paused if any of the following events occur in the mid-dose (n=2) or high-dose (n=2) sentinel groups and enrollment may resume only after the DSMB reviews the events and permits the study to continue.

1. Any grade 4 (Table 3) solicited local or systemic reaction considered to be at least possibly related to vaccination within 7 days after administration of the vaccine.
2. Two or more grade 3 (Table 3) solicited local or systemic reaction in the same dose group considered to be at least possibly related to vaccination that lasted at least 48 hours within 7 days after administration of the vaccine.
3. Any severe allergic reaction that is at least possibly related to vaccination within 24 hours after administration of the vaccine.

4. Any SAE within 28 days after administration of the vaccine considered to be at least possibly related to vaccination.
5. Any episode of myocarditis / pericarditis within 28 days after administration of the vaccine.
6. Any new episodes of elevated troponin, ECG and physical exam findings concerning for myocarditis / pericarditis within 28 days after administration of the vaccine.
7. Any death unless determined to be definitely not related to vaccination within 90 days after administration of the vaccine.

12.3 Halting Criteria for Full Group (Cohorts 1 and 2)

The study will be paused if any of the following events occur in the full group (standard (n=18), mid (n=18) and high dose (n=18) groups) and enrollment may resume only after the DSMB reviews the events and permits the study to continue.

1. Any grade 4 (Table 3) solicited local or systemic reaction in the mid or high-dose groups considered to be at least possibly related to vaccination within 7 days after administration of the vaccine.
2. Three or more grade 3 (Table 3) solicited local or systemic reaction in the same dose group considered to be at least possibly related to vaccination that lasted at least 48 hours within 7 days after administration of the vaccine.
3. Any three participants with severe allergic reaction that is at least possibly related to vaccination within 24 hours after administration of the vaccine.
4. Any SAE within 28 days after administration of the vaccine considered to be at least possibly related to vaccination.
5. Any episode of myocarditis / pericarditis within 28 days after administration of the vaccine.
6. Any new episodes of elevated troponin, ECG and physical exam findings concerning for myocarditis / pericarditis within 28 days after administration of the vaccine.
7. Any death unless determined to be definitely not related to vaccination within 90 days after administration of the vaccine.

If the halting criteria is triggered for the high-dose group and further enrollment of this group is not recommended by the study investigators, DSMB or IRB, the study will continue randomized enrollment into the mid-dose and standard-dose groups with a 1:2 ratio to complete the enrollment of 60 participants total. Since the expected immunogenicity difference between these two groups will be smaller, we will require more participants to detect a difference between these two groups. The 1:2 enrollment ratio into the mid-dose and standard-dose groups will even the distribution of participants into these two groups. The primary endpoint analysis for safety and reactogenicity will not be affected by a restriction of participants into the mid-dose and standard-dose groups.

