4 STUDY DESIGN

4.1 Study Overview

This is a Phase I/II open-label dose-finding trial among lung transplant recipients who received three or four mRNA vaccine doses (mRNA-1273 or BNT162b2) after lung transplantation to: standard-dose (50 ug), mid-dose (100 ug) or high-dose (200 ug) mRNA-1273 booster vaccine. Participants will be enrolled into three dose groups: 1) Standard-dose (50 ug) – 20 participants, 2) Mid-dose (100 ug) – 20 participants, 3) High-dose (200 ug) – 20 participants. The first 2 participants in both the mid-dose and high dose groups will be considered the ‘sentinel’ group. Participants in the sentinel group will receive the vaccine and undergo a 7-day observation period for safety and reactogenicity before additional participants are enrolled into that dose group.

Overall study enrollment will begin with the mid-dose sentinel group (n=2). During the observation period for the mid-dose sentinel group, we will enroll two participants into the standard-dose group. Once the mid-dose sentinel group completes their 7-day observation period without triggering halting rules and is approved to proceed by the DSMB, we will enroll the next 27 participants (Cohort 1) with a 2:1 randomization into the mid-dose (n=18) and standard-dose (n=9) groups.

Once all 20 participants have received their mid-dose vaccine without triggering halting rules and is approved to proceed by the DSMB, we will enroll the high-dose sentinel group (n=2). Once the high-dose sentinel group completes their 7-day observation period without triggering halting rules and is approved to proceed by the DSMB, we will enroll the next 27 participants (Cohort 2) with a 2:1 randomization into the high-dose (n=18) and standard-dose (n=9) groups. Thus, all 20 participants in the mid-dose group will be enrolled prior to enrollment of the high-dose group.

We will perform stratified randomization for the two cohorts based on: 1) the number of prior doses, and 2) prior receipt of any BNT162b2 vaccines. Randomization will be done by the UCLA Clinical and Translational Science Institute (CTSI) statistics team based on scheduled participants prior to the study visit. The 6 participants in the sentinel (n=4) and initial (n=2) groups (Table 1) will be assigned into the 3 groups based on their scheduled visit day.

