This clinical trial is designed to assess the safety, reactogenicity and immunogenicity of mid and high-dose mRNA-1273 vaccine among lung transplant recipients who have received three or four prior mRNA vaccines.

[figure not shown]
In-person visits will occur on Days 1 (booster vaccine), 7 and 30. Telephone visits will occur on Days 3, 90 and 180. Adverse events will be assessed in person (Days 1, 7 and 30) and by telephone calls (Days 3, 90 and 180). All follow-up visits will include a detailed review for serious adverse experiences (SAEs), adverse events of special interest (AESIs) and medically attended adverse events (MAAEs).

Table 1: Treatment Arms:

Groups will be enrolled as follows:	n	Dose
1) Mid-dose – Sentinel group	2	100 ug
2) Standard-dose – Initial group	2	50 ug
3) Cohort 1: 2:1 Randomization into		
Mid-dose group	18	100 ug
Standard-dose group	9	50 ug
4) High-dose – Sentinel group	2	200 ug
5) Cohort 2: 2:1 Randomization into		
High-dose group	18	200 ug
Standard-dose group	9	50 ug

Cohorts 1 and 2 will be randomized to their dose and considered the full group.

Figure 1. Study enrollment flow diagram

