14 STATISTICAL METHODS AND CONSIDERATIONS

14.1 General Considerations

Data collected in this study will be presented using summary tables and participant data listings. Continuous variables will be summarized using descriptive statistics, specifically the mean, median, standard deviation, minimum, and maximum. Categorical variables will be summarized by frequencies and percentages. Data Sets Analyzed:

- **Intent-to-Treat (ITT) Analysis Set**

The ITT analysis set includes all participants who are enrolled into a treatment (dose) group regardless of whether participants receive any study drug(s), or receive a different regimen from the regimen they were randomized to. Participants will be assigned into a dose group as described above.

- **Safety Analysis Set**

A safety analysis set will include data from participants who receive at least one dose of study treatment, with treatment assignments designated according to the actual treatment received. This analysis set will be used in the analyses of safety variables (primary endpoint) as well as study treatment administration.

- **Per-Protocol (PP) Analysis Set**

The PP analysis set includes data from participants in the ITT analysis set who meet the general criteria defining the target population for this study, are adherent to the protocol, are compliant with study drug treatment, and are evaluable for relevant efficacy endpoints. Treatment assignment will be designated according to the actual treatment received. The PP analysis set will be used in the analyses of the secondary endpoints. The PP analysis set will only include participants randomized to the dose-group (Cohorts 1 and 2, Figure 1). The PP analysis set will exclude participants in the sentinel mid-dose (n=2), sentinel high-dose (n=2) and initial standard-dose groups (n=2) who were not randomized to their dose-group. Participants who are found to have detectable anti-N-protein IgG antibody levels (representing prior infection) at their Day 1 (baseline) visit will be excluded from the PP analysis set.

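### The pause rules in 12.2 and 12.3 name 58 of 60 participants; a serious event (items 4-7) in the two initial standard-dose participants triggers no pause listed there

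*Combined protocol and SAP*

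**What the plan says.** Each list of pause rules opens by stating whom it covers.

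- Section 12.2 applies to events that "occur in the mid-dose (n=2) or high-dose (n=2) sentinel groups".
- Section 12.3, whose heading limits it to Cohorts 1 and 2, applies to events that "occur in the full group (standard (n=18), mid (n=18) and high dose (n=18) groups".
- Under Table 1 in section 4.1, "Cohorts 1 and 2 will be randomized to their dose and considered the full group".

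The initial standard-dose pair is a third category. Section 4.1 introduces it with "During the observation period for the mid-dose sentinel group, we will enroll two participants into the standard-dose group". The synopsis table and Table 1 give it its own line, and section 4.1 counts four sentinels and two initial participants separately. Section 14.1 removes from the per-protocol set the mid-dose sentinels together with the "sentinel high-dose (n=2) and initial standard-dose groups (n=2) who were not randomized to their dose-group".

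Four items in 12.3 need only one event to pause the study. Item 4 reads "Any SAE within 28 days after administration of the vaccine considered to be at least possibly related to vaccination". Items 5 and 6 cover myocarditis/pericarditis, and findings that raise suspicion of it, over the same 28 days. Item 7 reads "Any death unless determined to be definitely not related to vaccination within 90 days after administration of the vaccine". None of these four is restricted by dose, so they apply to the 50 ug participants in both cohorts. Item 1, in contrast, is restricted to the two higher doses.

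**The concern.** Automatic pause rules exist so that the response to a serious event does not depend on case-by-case judgment. By applying items 4-7 to the randomized 50 ug participants, the plan treats a single such event at the standard dose as sufficient reason to stop and ask the DSMB. Two people receiving the same dose of the same product fall outside that rule, and no reason is given. The low dose cannot be the reason, since it did not exempt the other 18. This looks like a drafting omission: the sentinel list was written for the two escalated doses and the full-group list for the randomized cohorts, and the initial pair is in neither.

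At stake is whether Cohort 1 enrollment would stop automatically after a serious related event or death in one of the first four people dosed. As 12.2 and 12.3 are written, it would if that person were a mid-dose sentinel but not if that person were in the initial standard-dose pair.

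**Working it through.** **Head count.** The plan's total is reproduced first from Table 1: 2 (mid-dose sentinel) + 2 (initial standard-dose) + 18 + 9 (Cohort 1) + 2 (high-dose sentinel) + 18 + 9 (Cohort 2) = 60, as stated.

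- Named in 12.2: 2 + 2 = 4.
- Named in 12.3: 18 + 18 + 18 = 54, which equals Cohorts 1 and 2 (27 + 27).
- Named in total: 4 + 54 = 58. Not named: 60 - 58 = 2.
- Standard dose: 2 + 9 + 9 = 20 participants, of whom 18 are named. The two missing are the initial pair.

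**Do the enrollment gates close the gap?** The first gate in section 4.1 opens Cohort 1 as follows: "Once the mid-dose sentinel group completes their 7-day observation period without triggering halting rules and is approved to proceed by the DSMB". It refers to the mid-dose sentinels and to the halting rules, and those rules do not name the pair. The next gate, before the high-dose sentinels, is worded around the 20 mid-dose participants. Between these two gates 18 + 9 = 27 participants enroll.

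**Do the pair's risk windows overlap Cohort 1 enrollment?** Let W be the window in days (28 for items 4-6, 90 for item 7). Let d be the day of the sentinel observation period on which a member of the pair is dosed (0 to 7), and D the DSMB review time in days. Assume both sentinels are dosed on one day. Cohort 1 can then open on day 7 + D, and the days left in the window are

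W - (7 + D - d).

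The documents do not give D, so a range is shown (D = 7 and D = 14 are assumptions):

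| D | Days left of 28 | Days left of 90 |
|---|---|---|
| 0 | 21 to 28 | 83 to 90 |
| 7 | 14 to 21 | 76 to 83 |
| 14 | 7 to 14 | 69 to 76 |

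The lower figure is for d = 0 and the upper for d = 7. The 28-day overlap disappears only when D reaches 21 (d = 0) to 28 (d = 7) days. If the sentinels are dosed on different days, the lower figures fall by the gap between them.

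No event probability is attached, because the documents give no rate for this population at this dose.

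**The case against.** The strongest reply is that the pair is well protected in practice. They receive 50 ug, which section 2 describes as the recommended booster dose. SAEs go to the IRB and FDA (11.2.1). AESIs must be reported within 7 days, and serious myocarditis or pericarditis within 72 hours (11.3), with SUSAR reporting as well (11.1). The DSMB oversees the whole study (5.3) and must approve before Cohort 1 opens. All of this stands, and it makes it unlikely that a serious event in the pair would go unexamined. But these are reporting and review duties. Section 5.3 says that halting and restarting need DSMB review; it gives no trigger.

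Three stronger readings are tempting and are not supported.

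- A reader might infer that the study could not, or would not, be paused for these two. The documents do not show that. The DSMB charter, which binds the investigator, is not among them. Section 11.4 (Medical Monitoring) is in the table of contents, but its text is missing from the copy used here. Either might contain a pause provision. Only the statement about 12.2 and 12.3 is supported.
- A reader might count everyone enrolled after the pair and the mid-dose sentinels, 27 + 2 + 27 = 56, as exposed. The last 29 enter only after further DSMB approvals, so the relevant figure is the 27 in Cohort 1.
- A reader might extend the point to items 1-3. Item 1 does not cover 50 ug in any cohort. Items 2 and 3 are count rules whose pools also leave out the sentinels of the other doses, so the pair's absence there is not anomalous in the same way.

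**Conclusion.** The gap is real as a matter of text and small in practice. Two of 60 participants, and two of the 20 at 50 ug, are outside items 4-7 and outside the sentinel list, while the other 18 at their dose are inside. No other text available gives them a pause trigger.

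The consequence is limited to Cohort 1: 27 participants, 9 of them at 50 ug, could continue to enroll after an event that would have paused the study had it occurred in a named participant. That the windows overlap rests on two assumptions: same-day dosing of the sentinels, and a DSMB review short enough to leave part of the window open. The 90-day window for deaths is the more robust of the two; even a 14-day review leaves at least 69 days.

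No endpoint, analysis set or dose comparison is affected. The change is worth making because it makes a safety rule consistent at very little cost, not because the risk is large.

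**What to change.** Leave the opening sentence of 12.3 and items 1-3 as they are, and add one sentence after the list: *Items 4-7 also apply to the initial standard-dose group (n=2).* Coverage for those items across 12.2 and 12.3 becomes 4 + 54 + 2 = 60 of 60.

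Adding the pair to the opening sentence of 12.3 looks simpler but would change two other rules. Item 2 would count over 20 participants at 50 ug but still over 18 at 100 ug and 200 ug, giving the lowest dose the largest pool. Item 3, which has no dose-group limit, would count over 56 rather than 54. The section heading would also no longer match its content. The separate sentence avoids all three.

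The cost is a very slightly higher chance of a study pause. Visits, data collected, sample size and analysis do not change. If the DSMB charter or section 11.4 already covers the pair, a cross-reference in 12.3 would serve instead.

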Axillary (underarm) swelling or tenderness ipsilateral to the side of injection	None	No interference with activity	Repeated use of over-the-counter (non-narcotic) pain reliever > 24 hours or some interference with activity	Any use of prescription (narcotic) pain reliever or prevents daily activity	Requires emergency room visit or hospitalization
Headache	None	No interference with activity	Repeated use of over-the-counter pain reliever > 24 hours or some interference with activity	Significant; any use of prescription pain reliever or prevents daily activity	Requires emergency room visit or hospitalization
Fatigue	None	No interference with activity	Some interference with activity	Significant; prevents daily activity	Requires emergency room visit or

Phase I/II, Open-label Dose-finding Trial of High-Dose mRNA-1273 Booster for Lung Transplant Recipients
Confidential

Reaction	Grade 0	Grade 1	Grade 2	Grade 3	Grade 4
					hospitalization
Myalgia (muscle aches all over body)	None	No interference with activity	Some interference with activity	Significant; prevents daily activity	Requires emergency room visit or hospitalization
Arthralgia (joint aches in several joints)	None	No interference with activity	Some interference with activity	Significant; prevents daily activity	Requires emergency room visit or hospitalization
Nausea/vomiting	None	No interference with activity or 1-2 episodes/24 hours	Some interference with activity or > 2 episodes/24 hours	Prevents daily activity, requires outpatient intravenous hydration (fluids given through blood veins)	Requires emergency room visit or hospitalization for low blood pressure
Chills	None	No interference with activity	Some interference with activity not requiring medical intervention	Prevents daily activity and requires medical intervention	Requires emergency room visit or hospitalization
Fever	< 38.0°C < 100.4°F	38.0 – 38.4°C 100.4 – 101.1°F	38.5 – 38.9°C 101.2 – 102.0°F	39.0 – 40.0°C 102.1 – 104.0°F	> 40.0°C > 104.0°F
Rash	No rash	Localized rash, without associated symptoms	Maculopapular rash (bumpy and red rash) covering < 50% body surface area	Generalized urticarial rash (hives or itchy rash) covering > 50% body surface area	Generalized exfoliative, ulcerative or bullous dermatitis (severe skin rash causing skin discoloration, peeling or blistering)

Reaction	Grade 0	Grade 1	Grade 2	Grade 3	Grade 4

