11.2 Serious Adverse Experiences (SAE)

An SAE is defined as any AE occurring at any dose that results in any of the following outcomes:

1. death
2. a life-threatening adverse experience
3. inpatient hospitalization or prolongation of existing hospitalization
4. a persistent or significant disability/incapacity
5. a congenital anomaly/birth defect

Other important medical events may also be considered an SAE when, based on appropriate medical judgment, they jeopardize the participant or require intervention to prevent one of the outcomes listed.

Participants will be instructed to call a study team line (attended 24-hours per day) if they experience any grade 4 symptom from the "Solicited Adverse Reactions and Grading" table (Table 3), any severe unsolicited AE (Table 4), or any SAE. The study team member will interview, document and triage the participant for further evaluation.

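### In the standard-dose full group, a related, non-serious grade 4 solicited reaction counts under neither halting item 1 nor item 2 of 12.3, so a worse set of reactions can avoid a pause that a milder set triggers

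*Combined protocol and SAP*

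**What the plan says.** The opening sentence of 12.3 pauses the study for listed events "in the full group (standard (n=18), mid (n=18) and high dose (n=18) groups", so the standard dose is within scope. Two items deal with solicited reactions:

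- Item 1: "Any grade 4 (Table 3) solicited local or systemic reaction in the mid or high-dose groups", at least possibly related, within 7 days. The standard dose is left out.
- Item 2: "Three or more grade 3 (Table 3) solicited local or systemic reaction in the same dose group", at least possibly related, lasting at least 48 hours, within 7 days. All dose groups are covered, but only grade 3 is named.

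Item 4 pauses for any related SAE within 28 days, in any dose group.

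The sentinel rule in 12.2 has no dose limit on grade 4: "Any grade 4 (Table 3) solicited local or systemic reaction considered to be at least possibly related to vaccination within 7 days". It applies only to the mid-dose and high-dose sentinels.

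In Table 3 (11.1), grades 3 and 4 are separate columns. The grade 4 entry for most reactions is "Requires emergency room visit or hospitalization", and fever above 40.0 C is grade 4 on temperature alone. The hospital criterion for an SAE in 11.2 is "inpatient hospitalization or prolongation of existing hospitalization"; an emergency visit is not listed.

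Section 4.1 gives Cohort 1 a "2:1 randomization into the mid-dose (n=18) and standard-dose (n=9) groups", and Cohort 2 adds another 9 at the standard dose.

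**The concern.** A pause rule should be monotone in severity: if a set of reactions triggers review by the Data and Safety Monitoring Board (DSMB), making one of them worse should not cancel the review. At the standard dose, 12.3 fails this test. Once a third reaction moves from grade 3 to grade 4 without becoming serious, it leaves the item 2 count and enters no other.

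Leaving 50 ug out of the single-event trigger may be deliberate, because the protocol describes it as the currently recommended booster dose. That does not explain item 2. There the plan chose to have a cluster of severe standard-dose reactions reviewed, and it gives no reason for a cluster to count for less when one member worsens. At stake is an automatic pause and DSMB review in the comparator arm.

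**Working it through.** **Step 1. Apply items 1 and 2 literally.** Take related reactions within 7 days, each lasting at least 48 hours, none an SAE.

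| Grade 3 | Grade 4 | Standard, as written | Mid or high, as written | Standard, item 2 counting grade 3 or higher |
|---|---|---|---|---|
| 3 | 0 | pause | pause | pause |
| 2 | 1 | no pause | pause | pause |
| 1 | 2 | no pause | pause | pause |
| 0 | 3 | no pause | pause | pause |
| 0 | 18 | no pause | pause | pause |
| 0 | 1 | no pause | pause | no pause |

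At the standard dose the first four rows grow more severe, and only the mildest pauses. The last row shows that the change leaves the item 1 exemption for 50 ug in place.

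**Step 2. Does another item catch these reactions?** Item 3 needs three participants with severe allergic reactions. Items 5 and 6 concern myocarditis or pericarditis and findings that suggest them. Item 7 concerns death. Only item 4 (related SAE) could apply generally, and it does not cover every case:

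- An emergency visit without admission, or fever above 40.0 C, is grade 4 in Table 3 but meets no SAE criterion in 11.2 automatically. The important-medical-event clause there depends on judgment.
- 11.2 tells participants to call for a grade 4 symptom or for an SAE, so it treats the two as different things.
- If every related grade 4 reaction were an SAE, item 4 would already pause for it and item 1 would have no function.

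**Step 3. Size, as illustration.** The plan states no figure for this rule and no grade 3 or 4 rates. Assumptions: one qualifying reaction per participant, independent participants, and grade 4 non-serious and counted whatever its duration. Let p3 and p4 be the per-participant probabilities. The chance that item 2 fires is P(X ≥ 3) = 1 − P(0) − P(1) − P(2), with X binomial(n, p). As written p = p3; after the change p = p3 + p4. The values of n are 9 (end of Cohort 1) and 18 (end of Cohort 2).

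Worked case, n = 18, p3 = 10%, p4 = 2%:

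- As written (p = 0.10): 1 − 0.150 − 0.300 − 0.284 = 0.266.
- After the change (p = 0.12): 1 − 0.100 − 0.246 − 0.285 = 0.369.
- Gap: 10.3 percentage points.

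| p3 | p4 | n = 9: as written, changed (gap) | n = 18: as written, changed (gap) |
|---|---|---|---|
| 10% | 2% | 5.3%, 8.3% (3.0) | 26.6%, 36.9% (10.3) |
| 10% | 1% | 5.3%, 6.7% (1.4) | 26.6%, 31.7% (5.1) |
| 5% | 1% | 0.8%, 1.4% (0.5) | 5.8%, 9.0% (3.2) |
| 5% | 0.2% | 0.8%, 0.9% (0.1) | 5.8%, 6.4% (0.6) |
| 3% | 0.5% | 0.2%, 0.3% (0.1) | 1.6%, 2.4% (0.8) |

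Gaps are percentage points, taken before rounding. For mid and high dose the gap is zero, because any related grade 4 reaction already pauses under item 1.

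**The case against.** The strongest reply is that the gap is narrow and the plan has other protection. The gap touches only the comparator dose. It needs at least three severe related reactions, at least one of them grade 4 and non-serious, with no other item met. Several grade 4 entries, such as necrosis or exfoliative dermatitis, would probably be judged serious in triple-immunosuppressed lung recipients and so pause under item 4. Grade 4 symptoms in any arm go to a 24-hour line, and an emergency visit is recorded as a medically attended event, so these reactions would be seen. The DSMB might in practice count grade 4 as at least grade 3, and its charter is not in the documents.

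Most of this stands as a limit on reach, but it does not close the gap. Seriousness beyond the listed criteria is a judgment, detection is not a pause, and nothing in 12.3 says that grade 4 counts under item 2.

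The figures also draw fair criticism. Item 2 counts reactions, whereas the illustration counts participants; one person with several concurrent grade 3 reactions could trigger it alone. Section 2 reports lower reactogenicity in lung recipients (any systemic reaction 46%, against 80% in healthy recipients, after the third dose), so low rates are plausible; the last two rows of the table show them. By n = 18 planned standard-dose enrolment is complete, so a trigger that late has little left to pause. These points bear on the size, not on the ordering in Step 1, which needs no rates.

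**Conclusion.** The concern holds. Followed literally, 12.3 is not monotone in severity for the standard-dose full group, and a more severe cluster can skip the DSMB review that a milder one requires. This rests on the wording alone.

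The practical size is modest and uncertain, since it depends wholly on assumed rates and on the one-reaction-per-participant simplification. Mid dose, high dose and the sentinel groups are unaffected, as is the step to 200 ug, which 4.1 ties to the mid-dose participants. If high dose were stopped, 12.3 would send remaining enrolment 1:2 to mid and standard dose, so the affected group would grow. The change should be made because a stated safety rule gives a perverse result and is simple to correct.

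**What to change.** In item 2 of 12.3, insert 'or higher' after 'grade 3', and state that the 48-hour condition applies to grade 3 reactions while any related grade 4 reaction counts regardless of duration. Adding 'or higher' alone would restore the ordering for reactions of equal duration. Dropping the duration condition for grade 4 matches item 1 of 12.3 and item 1 of 12.2, neither of which has one. Item 1 can stay as it is.

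The cost is a short wording change, repeated in the DSMB charter if the charter restates the rule, and submitted as an amendment with prior written IRB approval under 15.8. The downside is a slightly higher chance of a pause for DSMB review, in clusters at least as severe as those that already require one.
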